**Table 3–1: Treatment group assignment for the TFLs**

TFL group	PS0016 randomized treatment group			PS0018 dose at onset			Dose adjustment group	
	BKZ 320mg + PBO	BKZ 320mg	All Subjects	BKZ 160mg Q4W	BKZ 320mg Q4W	All BKZ	Non- adjuster	Adjuster
Subject disposition	X	X	X					
Protocol deviations	X	X	X					
Demographics	X	X	X					
Medical history	X	X	X					
Prior/concomitant medications	X	X	X					
Compliance	X	X	X					
Exposure				X	X	X		
AEs a	X	X	X	X	X	X	X	X
Safety data (including vital signs, ECGs and laboratory tests)	X	X						
Efficacy (except PASI)	X	X	X					
PASI	X	X	X				X	X
Pharmacokinetic data	X	X						
ADA	X	X						

ADA= anti-bimekizumab drug antibody; AE=adverse events; ECG= electrocardiogram; IMP= investigational medicinal product; Q4W= every four weeks; TFL= tables, figures, and listings.

aSelect tables presenting TEAEs by PS0016 randomized treatment group and Dose adjustment group, as defined in [Section 11.2.3](#).

### **3.7 Center pooling strategy**

The data from different sites will be pooled for all analyses. There will be no stratification by site or country performed.

### **3.8 Coding dictionaries**

Adverse events (AEs) and medical history will be coded using the Medical Dictionary for Regulatory Activities (MedDRA®), Version 19.0.

Medications will be coded according to the World Health Organization Drug Dictionary (WHODD [September 2015]). Medical procedures will not be coded

### **3.9 Changes to protocol-defined analyses**

Change from Baseline in physical examination is listed as a secondary safety variable, in [Section 2.2.1.2](#). Only whether the physical examination was performed and the date it was performed is recorded on the CRF. Thus no summaries for the change from Baseline in physical examination will be provided.”

For the continuous efficacy variables based on the change from Baseline (PASI, BSA, and HADS), imputation for missing values in the protocol is based on multiple imputation (MI) via the Markov Chain Monte Carlo (MCMC) method. However, due to the smaller sample size in PS0018 this may cause problems in the algorithm. For this reason and for consistency with the PS0016 SAP, imputation in PS0018 will instead be based on last observation carried forward (LOCF).

For the dose adjustment groupings, the single and multiple dose adjuster groupings will be combined for summary purposes, unless stated otherwise.

## **4 STATISTICAL/ANALYTICAL ISSUES**

### **4.1 Adjustments for covariates**

There will be no adjustments for covariates.

### **4.2 Handling of dropouts or missing data**

If a subject does not achieve a PASI50 at Week 12 or later during the open-label treatment period then they will be withdrawn from the study, in order to provide the subjects with alternative therapy to treat the condition. Therefore, in many cases, missing data due to study treatment discontinuation will occur. For missing continuous data single imputation by means of LOCF will be applied.

Missing data for the binary response variables will be imputed using non responder imputation (NRI), ie subjects with a missing score at a specific visit will be considered as non-responders for the summaries. This will include visits after the point of withdrawal.

Supportive summaries will be based on observed case data and will be repeated for all analyses presented with imputation.

Missing data will be handled as described in the sections below for efficacy, safety and PK results. No other imputations will be performed.

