#### **3.2 Secondary objectives**

Secondary objectives of the study are:

- To assess the safety and tolerability of increasing the dose of bimekizumab from 160mg Q4W to 320mg Q4W for subjects with an inadequate response at Week 12
- To assess PK of bimekizumab
- To assess the immunogenicity of bimekizumab
- To assess the efficacy of open-label bimekizumab 160mg Q4W administered over 48 weeks

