## 5 STUDY DESIGN

### 5.1 Study description

PS0018 is a multicenter, 48-week, open-label extension study to assess the long-term safety, tolerability, and efficacy of bimekizumab in eligible adult subjects with moderate to severe chronic plaque psoriasis who participated in PS0016.

During the Open-Label Treatment Period, subjects will attend study visits at the site Q4W for study assessments and administration of bimekizumab by study site staff through Week 48. Following completion or early withdrawal from the 48-week Open-Label Treatment Period, subjects will return for a SFU Visit 20 weeks after their last dose of bimekizumab. Subjects withdrawing early from the study will undergo the Early Withdrawal Visit assessments and will enter the SFU Period.

Bimekizumab will initially be administered at a dose of 160mg Q4W subcutaneously (sc) during the 48 week Open Label Treatment Period. There will be an option to increase the dose to 320mg Q4W at the discretion of the Investigator if the subject's PASI response is  $\geq 50\%$  to  $< 75\%$  reduction from the Baseline of PS0016 at Week 12 or later. If the subject's disease is adequately controlled on the 320mg Q4W dose, they may return to 160mg Q4W at the discretion of the Investigator. The decision to return to 160mg Q4W dosing should be based upon treatment response, tolerability, and Investigator discretion, with the aim to use the dosing regimen that achieves the optimal benefit-risk for each subject. If a subject does not achieve a PASI50 at Week 12 or later then they will be withdrawn from the study.

A schedule of study assessments is presented in [Table 5–1](#).

---

A study schematic diagram of PS0018 is presented in [Figure 5–1](#).

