#### 2.1.2 Secondary objectives

Secondary objectives of the study are:

- To assess the safety and tolerability of increasing the dose of bimekizumab from 160mg every four weeks (Q4W) to 320mg Q4W for subjects with an inadequate response at Week 12
- To assess pharmacokinetics (PK) of bimekizumab
- To assess the immunogenicity of bimekizumab
- To assess the efficacy of open label bimekizumab 160mg Q4W administered over 48 weeks

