## 2.3 Study design and conduct

PS0018 is a multicenter, 48-week, open-label extension study to assess the long-term safety, tolerability, and efficacy of bimekizumab in eligible adult subjects with moderate to severe chronic plaque psoriasis who participated in PS0016.

During the Open-Label Treatment Period, subjects will attend study visits at the site Q4W for study assessments and administration of bimekizumab by study site staff through Week 48. Following completion or Withdrawal (WD) from the 48-week Open-Label Treatment Period, subjects will return for a Safety Follow-Up (SFU) Visit 20 weeks after their last dose of bimekizumab. Subjects withdrawing early from the study will also undergo the WD assessments and will enter the SFU Visit.

Bimekizumab will initially be administered at a dose of 160mg Q4W subcutaneously (sc) during the 48 week Open-Label Treatment Period. There will be an option to increase the dose to 320mg Q4W at the discretion of the Investigator if the subject's PASI reduction is  $\geq 50\%$  to  $< 75\%$  from the PS0016 Baseline at Week 12 or later in the PS0018 study. If the subject's disease is adequately controlled on the 320mg Q4W dose, they may return to 160mg Q4W at the discretion of the Investigator. The decision to return to 160mg Q4W dosing should be based upon treatment response, tolerability, and Investigator discretion, with the aim to use the dosing regimen that achieves the optimal benefit-risk for each subject. If a subject does not achieve a PASI50 at Week 12 or later during the PS0018 study based on change from PS0016 Baseline then they will be withdrawn from the study.

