### **3.6 Treatment assignment and treatment groups**

Treatment assignment for the SS and PK-PPS will be according to the actual treatment received in PS0018, unless stated otherwise in [Table 3–1](#). Analyses of efficacy data (based on the FAS) will be conducted according to the PS0016 randomized treatment group.

Subjects receiving the incorrect treatment (for example due to a dosing error) at a particular visit will be excluded from the PK-PPS as this would be considered as an important protocol deviation. Subjects may be excluded from the analysis at a particular visit (or visits) only, following discussion at the DEM.

Listings will be presented by subjects as randomized in PS0016. Summaries will be presented by treatment group and overall where applicable. See [Table 3–1](#) for the treatment assignment of the 3 different sets of treatment groups.

---

In the TFLs the treatment groups based on the PS0016 randomized treatment group will be displayed as follows, where BKZ refers to bimekizumab and PBO refers to placebo:

- BKZ 320mg + PBO
- BKZ 320mg
- All Subjects

In the TFLs the treatment groups based on the actual PS0018 treatment received (ie PS0018 dose at onset of event or measurement) will be displayed as follows:

- BKZ 160mg Q4W
- BKZ 320mg Q4W
- All BKZ

Lastly there will be the grouping based on dose adjustment in PS0018 defined as follows:

- Nonadjusters – This group consists of subjects who do not experience a dose adjustment during the study.
- Single adjusters – This group consists of subjects who experience just one dose adjustment during the study. Per the protocol, if just a single adjustment occurs, then that adjustment must go from bimekizumab 160mg Q4W to 320mg Q4W.
- Multiple adjusters – This group consists of subjects who experience more than 1 dose adjustment during the study. This means that the subjects in this group dose adjust from bimekizumab 160mg Q4W to 320mg Q4W and then adjust back to 160mg Q4W (with further dose adjustments possible).

For summary purposes, the single and multiple adjuster groupings will be combined.

The treatment group labels and tabulation requirements for each data type are displayed in [Table 3–1](#) **Error! Reference source not found.**

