The highest potential PASI score is 72 for severe disease; the lowest score is 0 which indicates no psoriatic lesions are present. The PASI scores are considered as a continuous variable and will be calculated and presented to 1 decimal place in the listings. The percentage change in PASI score from PS0016 Baseline will be calculated as follows:

$$\text{Percentage change from PS0016 Baseline} = 100 \times [(\text{PS0018 PASI} - \text{PS0016 Baseline PASI}) / \text{PS0016 Baseline PASI}] \quad [8]$$

Thus, for subjects with an improvement in the PASI score, the percentage will be negative. For subjects with a worsening in the PASI score, the percentage will be positive.

A categorical response variable, such as PASI90, is defined to be equal to 1 if the percentage improvement from PS0016 Baseline in the PASI scores is 90% or greater and 0 if the percentage improvement from PS0016 Baseline is less than 90%. This definition is introduced for the purpose of identifying subjects who respond to the treatment (1 = responder, 0 = non-responder). Similarly, the categorical secondary efficacy variables PASI50, PASI75, and PASI100 response are equal to 1 for subjects with improvements of 50% or greater, 75% or greater and 100% from PS0016 Baseline in PASI score, respectively (and equal to 0 otherwise).

If a subject does not achieve PASI50 at Week 12 or reverts below PASI50 later during the PS0018 study based on a change from PS0016 Baseline then they will be withdrawn from the study.

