Furthermore, a supportive analysis specifically for adjusters will be performed in which PASI score will be summarized by visit, where Baseline is recalibrated for each individual subject and defined as the visit where the bimekizumab 320mg Q4W dose is initiated. The visits summarized

will be in weeks relative to when the bimekizumab 320mg Q4W dose was started as opposed to the scheduled week of the PS0018 assessment. These summaries will be based on observed data only.

The PASI50, PASI75, PASI90, and PASI100 responses are based on at least 50%, 75%, 90%, and 100% improvement from Baseline in the PASI score. Thus, the following will apply:

- If the percentage improvement is  $\geq 50\%$  then the subject is a PASI50 responder
- If the percentage improvement is  $\geq 75\%$  then the subject is a PASI75 responder (and is a PASI50 responder also)
- If the percentage improvement is  $\geq 90\%$  then the subject is a PASI90 responder (and is a PASI50 and PASI75 responder also)
- If the percentage improvement is 100% then the subject is a PASI100 responder (and is a PASI50, PASI75 and PASI90 responder also)

The number and percentage of subjects achieving a PASI50, PASI75, PASI90, and PASI100 response will be tabulated by visit and overall and by PS0016 randomized treatment group and by Dose adjustment. The 95% CI for the percentage of responders will be calculated using a Wilson approximation and be included in the tabulation.

In addition, the percentage of responders (including 95% CI) will be plotted at each PS0018 visit for each response variable. Separate plots will be presented for each of PASI50, PASI75, PASI90 and PASI100 with both treatment groups overlaid on the same plot. These plots will be presented by PS0016 randomized treatment and by Dose adjustment separately.

For the purpose of the tabulation the lower and upper 95% confidence limits for the percentage of responders will be truncated at 0 and 100% respectively.

Missing data will be imputed using NRI as described in [Section 4.2.1.1](#). Subjects with missing data will be regarded as non-responders for the PASI50, PASI75, PASI90, and PASI100 variables.

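### From Week 16 to Week 48 no planned responder table estimates response on 160mg Q4W, the dose that the secondary efficacy objective names

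*SAP*

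**What the plan says.** - **Objective.** Protocol 3.2: "To assess the efficacy of open-label bimekizumab 160mg Q4W administered over 48 weeks". SAP 2.1.2 repeats it. Protocol 5.4 gives, as one reason for starting at 160mg, that it will provide data on a dose reduction, so the 160mg result is a purpose of the design.
- **Dose change.** Protocol 5.1: "There will be an option to increase the dose to 320mg Q4W at the discretion of the Investigator". The option opens at Week 12 for a PASI reduction of at least 50% but under 75%, and a later return to 160mg is allowed. SAP 2.3 says the same.
- **Grouping.** SAP 3.6: "Analyses of efficacy data (based on the FAS) will be conducted according to the PS0016 randomized treatment group". In the SAP table that assigns treatment groups to outputs, columns for PS0018 dose are marked for exposure and AEs only. The nonadjuster/adjuster columns are marked for PASI and AEs, but not for the other efficacy variables.
- **Response.** SAP 8.1.1 defines PASI90, for example, by whether "the percentage improvement from PS0016 Baseline in the PASI scores is 90% or greater". The definition does not refer to the dose being taken. IGA response in SAP 8.1.2 has no dose condition either.
- **Non-response.** SAP 4.2: "subjects with a missing score at a specific visit will be considered as non-responders for the summaries". SAP 4.2.1.1 and 4.2.1.3 apply this to PASI and IGA, including visits after withdrawal.
- **Tables.** SAP 8.2.1: PASI50/75/90/100 "response will be tabulated by visit and overall and by PS0016 randomized treatment group and by Dose adjustment". SAP 8.2.3 tabulates IGA response by PS0016 arm and overall only.

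**The concern.** Subjects who do less well on 160mg leave that dose by two routes. Those below PASI50 are withdrawn, and non-responder imputation then scores them as failures. Those between PASI50 and PASI75 may go to 320mg. They still have observed scores, so no rule touches them, and a PASI75 first reached on 320mg enters the numerator.

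The dose-adjustment split looks like the remedy but is not one. Nonadjusters are defined by what happens after baseline over the whole study, and the subjects taken out are those whose 160mg response was judged insufficient.

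At stake is the answer to a stated secondary objective. The SAP attributes AEs to the dose at onset (SAP 11.2.1) but has no counterpart for efficacy.

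**Working it through.** **1. Can any planned responder table give the 160mg result?**

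- *All subjects, through Week 12:* yes. Protocol 8.4 places drug administration after all other assessments at Week 12, and no increase is possible earlier.
- *All subjects or PS0016 arm, Weeks 16 to 48:* no. Visits on both doses are counted alike.
- *PASI nonadjusters:* no. Increased subjects are missing from numerator and denominator. Subjects withdrawn below PASI50 who were never increased stay in as non-responders, as do partial responders whom the investigator did not increase.
- *PASI adjusters:* no. The column mixes 160mg and 320mg visits and pools single with multiple adjusters (SAP 3.6).
- *Supportive adjuster analysis (SAP 8.2.1):* no. It starts at the first 320mg visit and summarizes score, not response.
- *IGA:* no dose-adjustment split.

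**2. Size.** There is no figure in the plan to reproduce. Enrolment of up to 45 is carried over from the feeder study (Protocol 14.7), and neither an escalation rate nor a response rate is given. All counts below are assumptions, with FAS = 45.

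At Week 48, let N = FAS, e = subjects ever increased, x = increased subjects responding, and R = responders never increased.

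- All-subject row = (R + x)/N
- Nonadjuster column = R/(N − e)
- Response without dose increase = R/N
- Excess of the all-subject row = x/N, which is never negative
- Nonadjuster column ÷ (R/N) = N/(N − e), which is above 1 whenever e > 0

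With N = 45, x/N is 0 for x = 0, 2/45 = 4.4 points for x = 2, 3/45 = 6.7 points for x = 3 and 7/45 = 15.6 points for x = 7.

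| Assumed e, x, R | All-subject row | Nonadjuster column | Without dose increase |
|---|---|---|---|
| 2, 2, 30 | 32/45 = 71.1% | 30/43 = 69.8% | 30/45 = 66.7% |
| 5, 3, 30 | 33/45 = 73.3% | 30/40 = 75.0% | 30/45 = 66.7% |
| 9, 5, 31 | 36/45 = 80.0% | 31/36 = 86.1% | 31/45 = 68.9% |
| 10, 7, 30 | 37/45 = 82.2% | 30/35 = 85.7% | 30/45 = 66.7% |

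Over a wider grid (e = 5, 9 or 14; 40% to 80% of increased subjects responding; about 70% or 85% of nonadjusters responding), the all-subject row is 4.4 to 24.4 points above R/N, and the nonadjuster column 7.8 to 26.1 points above it.

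In the third row of the table, the Wilson 95% intervals are 66.2% to 89.1% for the all-subject row and 54.3% to 80.5% for R/N. They overlap, as expected with 45 subjects, but the difference between the two quantities is systematic.

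**3. Earlier visits.** The factor N/(N − e) is exact at Week 48 only. At Weeks 16 to 44 the nonadjuster column also leaves out subjects who increase later and are still on 160mg, so the wanted proportion cannot be recovered from it.

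**The case against.** The best defence is that the planned tables answer a legitimate question. Protocol 14.5 says that the efficacy summaries show maintenance of the drug's effect, without naming a dose, and the impact of dose adjustments. No efficacy column is labelled 160mg. On a start-at-160mg, increase-if-needed reading, the all-subject table is the right one. This stands as a reason to keep those tables, but the objective is not worded that way in either document.

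It can also be said that R/N for PASI at Week 48 follows from the nonadjuster responder count and the FAS count, and that the listings flag time points on 320mg (SAP 3.1). That is true, but no table prints the figure, and the division fails for IGA and for earlier visits.

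Finally, the objective is secondary, the study is uncontrolled and descriptive, and safety is primary. This limits the weight of the point.

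A reader might infer more than the documents support:

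- *That no table informs 160mg efficacy at all.* The all-subject tables through Week 12 do.
- *That nonadjusters exclude all 160mg failures.* They lose only the increased subjects. Under Protocol 5.1 these are PASI50 responders when increased, so the upward selection is argued for PASI75/90/100 and not for PASI50. The trigger is PASI alone, so an increased subject need not be an IGA non-responder.
- *That adjusters are always on 320mg after the increase.* They may return to 160mg.
- *That non-responder imputation is wrong.* It is sound for missing scores; escalation simply falls outside it.
- *That the gaps measure how far 160mg alone is overstated.* R/N counts an increase as failure. A partial responder left on 160mg might have improved, and the documents cannot say how often.

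**Conclusion.** The point holds for Weeks 16 to 48. Neither the all-subject responder tables nor the PASI nonadjuster column estimates response on 160mg Q4W, and both lie at or above the Week 48 proportion responding without a dose increase. The direction follows from the definitions; the size rests on assumed counts. The excess of the all-subject row could be nil or a few points if few increased subjects respond, about 7 points with three such responders in 45 and about 16 points with seven. The change should be made, but as an added descriptive summary with clear labels; the current tables contain no error of calculation.

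**What to change.** In SAP 8.2.1 and 8.2.3, with a cross-reference in 4.2, add a by-visit summary in the full FAS of PASI75, PASI90, PASI100 and IGA response without dose increase.

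- Count every visit after the first 320mg dose as non-response. The assessment made before that dose on the same day keeps its observed value.
- State that visits after a return to 160mg also count as non-response, because the quantity is response maintained on 160mg without a dose increase.
- If PASI50 is shown, label it PASI50 without dose increase, since subjects who increase are PASI50 responders at that point.
- Keep the current tables, labelled as results of the flexible 160/320mg regimen.

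If the sponsor intends only the flexible regimen, reword the objective in SAP 2.1.2 to 160mg Q4W with optional increase, and record this in SAP 3.9 because Protocol 3.2 has the same wording.

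The LOCF summaries of PASI, BSA and HADS scores mix doses in the same way. The non-response rule does not carry over to them, so the SAP should at least label them as flexible-regimen results.

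The cost is one derivation rule and one extra set of descriptive tables, using the dose flags already planned for the listings, and a stated response rate that will be lower whenever increased subjects respond.

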## **4.2.1 Efficacy data**

### **4.2.1.1 Psoriasis Area and Severity Index**

Missing data for the individual items of the PASI score will be imputed as described in [Section 8.1.1](#) in order to calculate the PASI score at each visit.

For the summaries of the observed, change and percentage change from PS0016 Baseline in PASI score, LOCF will be applied to address the issue of missing scores as described in [Section 4.2](#). There will be no imputation of missing individual item scores in the summaries for the PASI; LOCF will apply to the overall PASI score only.

Missing data for the binary response variables (PASI50, PASI75, PASI90 and PASI100) will be imputed using NRI for the summaries. This will include visits after the point of withdrawal.

### **4.2.1.2 Body surface area**

Missing body surface area (BSA) data will be handled using LOCF as described in [Section 4.2](#).

### **4.2.1.3 Investigator's Global Assessment**

There will be no imputation of missing individual data for the IGA score. For the responder analysis, missing data will be imputed using NRI, ie subjects with missing data at a specific visit will be considered as non-responders for the analysis. This will include visits after the point of withdrawal if applicable.

### **4.2.1.4 Hospital Anxiety and Depression Scale**

Missing data for the individual items of the HADS will be imputed as described in [Section 8.1.3](#) in order to calculate the HADS-A and HADS-D scores at each visit. Missing HADS-A and HADS-D domain scores will be handled using LOCF as described in [Section 4.2](#).

